IRB Minimal Risk Protocol Template

Note: If this study establishes a human specimen repository (biobank) for research purposes, do not use this template. Use the Mayo Clinic Human Specimen Repository Protocol Template found on the IRB home page under Forms and Procedures at http://intranet.mayo.edu/charlie/irb/

First-time Use: Use this template to describe your study for a new IRB submission.

- 1. Complete the questions that apply to your study.
- 2. Save an electronic copy of this protocol for future revisions.
- 3. When completing your IRBe application, you will be asked to upload this document to the protocol section.

Modification: To modify this document after your study has been approved:

- 1. Open your study in IRBe. Click on the study 'Documents' tab and select the most recent version of the protocol. Save it to your files.
- 2. Open the saved document and activate "Track Changes".
- 3. Revise the protocol template to reflect the modification points, save the template to your files
- 4. Create an IRBe Modification for the study and upload the revised protocol template.

General Study Information

Principal Investigator: [name]

Study Title: A Randomized-Controlled trial comparing long-acting and short-acting local anesthetics at the time of penile prosthesis placement.

Protocol version number and date: Version 2; July 21, 2021

Research Question and Aims

Hypothesis:

Local anesthesia with liposomal bupivacaine administered at the time of penile prosthesis placement will reduce postoperative opioid use and decrease post-operative pain when compared with administration of ropivacaine.

Aims, purpose, or objectives:

This study aims to determine if using liposomal bupivacaine, when compared with ropivacaine, for postoperative pain control in patients undergoing surgical placement of a 3-piece inflatable penile prosthesis is associated with less overall opioid use and lower postoperative pain scores during the early postoperative period. Variables to be analyzed will include pre- and postoperative pain and anxiety scores, in-hospital (if-applicable) and home opioid use postoperatively, and adverse intraoperative, perioperative, and postoperative events.

Background (Include relevant experience, gaps in current knowledge, preliminary data, etc.):

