Liposomal bupivacaine (LB) is a long-acting local anesthetic that has been shown to promote local pain control in the postoperative period for up to 72 hours, as compared to traditional local anesthetic agents with half-lives ranging from 1-6 hours. The prolonged pain control duration is the result of suspending the bupivacaine within a lipid vessel that creates slow release of the medication within tissues over time. Within the realm of urology very few studies have assessed outcomes in patients who receive perioperative LB. A study by Cotta et al from 2016 retrospectively explored their experience with LB (n=13) compared with those receiving local bupivacaine (n=24) for anesthesia during penile prosthesis placement.[6] The authors found that patients receiving LB used significantly fewer opioids postoperatively. Two additional studies by Alom et al and [name] et al described LB for use with office-based surgical procedures involving the penis and scrotum, although outcomes related to pain control were not specifically evaluated.[7,8] Finally, a recent study by Taniguchi and Mulhall showed that LB did not adversely impact systemic hemodynamics when administered within the corpora cavernosa of patients at the time of penile prosthesis placement, supporting the safety of this medication in the perioperative setting.[9]

It has been our experience that LB optimizes pain control in the postoperative setting when administered at the time of penile prosthesis placement. This has become a routine part of clinical practice. However, LB results in added expense, and to date there has never been an adequately powered prospective study comparing outcomes between LB and other shorter-acting local anesthestics to determine if this added expense is justified. Therefore, we intend to assess perioperative and postoperative outcomes including safety and pain control in patients who receive local anesthesia with LB versus ropivacaine at the time of penile prosthesis placement.

References:

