Study participants will be randomized to one of two study arms. Arm 1 will receive 40 mL of ropivicaine to be used for local anesthetic infiltration. Arm 2 will receive 40 mL of Liposomal bupivacaine (20 mL Exparel + 10 mL 0.25% bupivacaine) to be used for local anesthetic infiltration. The patient will be blinded to which study arm he is randomized to, but the surgeon will be aware (i.e. single blind). The specific agent (determined by study randomization) will be ordered by the performing surgeon through the "prep for case" inflatable penile prosthesis order set within EPIC. Two standardized order sets will be shared amongst the three performing surgeons and will also include standardized perioperative medication administration per a previously published enhanced recovery protocol (see reference #5 – Lucas et al).

Local anesthetic will be administered via a standard protocol at the time of penile prosthesis surgery. The block itself will include pudendal, scrotal, dorsal penile, and inguinal nerve blocks. The remainder of the penile prosthesis surgery will be per standard practice, with all surgeons currently utilizing a similar penoscrotal

approach. Of note, patients who currently receive intraoperative LB routinely wear a disposable bracelet with information for medical professionals regarding the recent receipt of this medication. This is worn for 72-96 hours postoperatively. For the study protocol, we will work with the perioperative nursing team to apply a similar bracelet describing the research study and acknowledging that each patient may have received LB versus ropivacaine during the surgery.

If the study coordinator is unable to meet with the patient to review consent, they will be a digital consent via email. The patient will be contacted by telephone and read a script about study participation. Patients will then have the ability to sign the consent form with their personal device. These digital consent forms will be stored in Ptrax.

If patients decide to consent digitally, they will be asked to complete the baseline requirements over the phone. These documents are the baseline anxiety inventory and the pain catastrophizing scale which will be recorded by the study coordinator.

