Preoperative patient data including pertinent demographics as well as a baseline anxiety inventory and pain catastrophizing scale will be collected. They will also receive a medication log to track their narcotic intake until post-operative day 14. The patients will be followed-up by phone call or through electronic correspondence (RedCap) on post-operative days 3, 7, and 14. Participants in the study will be allowed to completed the questionnaires through RedCap with a +/- 2 day allowance on completion to avoid any study deviation. This follow-up will be obtained by the performing surgeons and/or the research office coordinator. At these planned follow-up intervals, patients will be evaluated using the Visual Analog Pain Scale (daily maximum and minimum) and visual analogue anxiety scale (daily maximum and minimum). In addition their pain control regimen (quantities of Tylenol, anti-inflammatories, and opioid pain medication) will be analyzed. Patients will be instructed to bring their medication bottles to their 3 week follow-up. Patient satisfaction with overall postoperative pain control will be measured based on subjective response. Finally, the duration of local anesthetic effect will be measured based on patient report.

Subject Information

Target accrual is the proposed total number of subjects to be included in this study at Mayo Clinic. A "Subject" may include medical records, images, or specimens generated at Mayo Clinic and/or received from external sources.

Target accrual: 130 patients (65 patients in each treatment arm) – this accounts for the necessary statistical power plus an anticipated approximately 20% dropout rate.

Subject population (children, adults, groups): Patients with medication-refractory erectile dysfunction undergoing penile prosthesis placement at Mayo Clinic in Rochester by Drs. [name], [name], and [name].

Inclusion Criteria:

- Men undergoing 3-piece inflatable penile prosthesis placement under general anesthesia at Mayo Clinic

 Rochester
- 2. \geq 18 years old

Exclusion Criteria:

- 1. History of opioid exposure within the preceding 90 days prior to surgery (based on patient-report, review of the electronic medical record, and NMP prescribing database review)
- 2. Current or prior history of alcohol or drug abuse (illicit or prescription)
- 3. History of chronic pain conditions (chronic musculoskeletal pain, fibromyalgia, central sensitization, chronic pelvic pain syndrome, etc.)

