Note: The Date Range must include the period for collection of baseline data, as well as follow-up data, if applicable.

The study involves data that exist at the time of IRB submission **and** data that will be generated after IRB submission. Include this activity in the Methods section. Examples

- The study plans to conduct a retrospective chart review and ask subjects to complete a questionnaire.
- The study plans to include subjects previously diagnosed with a specific disease and add newly diagnosed subjects in the future.

The study will use data that have been collected under another IRB protocol. Include in the Methods section and enter the IRB number from which the research material will be obtained. *When appropriate, note when subjects have provided consent for future use of their data and/or specimens as described in this protocol.*

Enter one IRB number per line, add more lines as needed

🗌 Data	Specimens Data & Specimens	
🗌 Data	Specimens Data & Specimens	
🗌 Data	Specimens Data & Specimens	

Data Analysis

Power analyses may not be appropriate if this is a feasibility or pilot study, but end-point analysis plans are always appropriate even if only exploratory. Provide all information requested below, or provide justification if not including all of the information.

Power Statement: A total sample size of 110 (55 per arm) provides 90% power to detect a clinically relevant difference in discharge prescription opioids of 37.5 OME, based on a two-sample, two-sided, equal-variance t-test with significance alpha level 0.05, and assuming a common standard deviation of 60 OME. With an anticipated drop-out rate of 18%, total sample size will be 130 (65 per arm).

Data Analysis Plan:

Patient data will be recorded and stored in a study-specific database through RedCap. This database will be created by the primary investigator. At the completion of the study, statistical analyst support will be used to perform the final data analysis.

Preoperative data collection:

-State-Trait Anxiety inventory (attachment 1) -Pain Catastrophizing scale (attachment 2)

Postoperative days 3,7,14 data collection:

-Visual-analogue pain score (attachment 3)

-Visual-analogue anxiety score (attachment 4)

-Analgesic quantities (acetaminophen, meloxicam, ibuprofen, gabapentin, oxycodone, tramadol)

Endpoints

Primary:

1. Postoperative opioid pain medication use (number of oral morphine equivalents consumed per day and total number)

Secondary:

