- 2. Postoperative pain scores (Maximum and minimum on visual analogue pain scale of 0-10) on postoperative days3, 7, 14
- 3. Postoperative non-narcotic pain medication use (non-steroidal anti-inflammatories, acetaminophen, gabapentin)
- 4. Postoperative anxiety scores (Maximum and minimum on visual analogue anxiety scale of 0-10) on postoperative days 0-7
- 5. Adverse perioperative events cardiovascular parameter changes
- 6. Patient satisfaction (subjective, patient reported)
- 7. Duration of pain control from local anesthetic

Attachments:

- -Visual-analog pain scale (attachment 1)
- -Visual-analog anxiety scale (attachment 2)
- -State-Trait Anxiety inventory (attachment 3)
- -Pain catastrophizing scale (attachment 4)
- -Perioperative analgesia protocol (attachment 5)
- -Preoperative, perioperative, and postoperative clinical variables of interest (attachment 6)
- -Proposed budget (attachment 7)

Anxiety Scores Prior to the procedure

Mark (X) the point on the scale that best describes how you are feeling at the moment. Use the Dowrick facial anxiety scale to assist you.

Edward Dowrick © 2016 Anxiety Level Self-assessment and facial anxiety scale female

After the procedure

Mark (X) the point on the scale that best describes how you are feeling at the moment. Use the Dowrick facial anxiety scale to assist you.

Edward Dowrick © 2016 Anxiety Level Self-assessment and facial anxiety scale female

State Trait Anxiety Inventory

How do you feel RIGHT NOW? Read each statement and select the number which most closely indicates how you feel right now. There are no right or wrong answers. Please give the answer which seems to describe your present feelings best.

	1	2	3		4		
	Not at all	A little	Some	what	Ver	y Much So	
1.	I feel calm		1	2	3	4	
2.	I feel secure		1	2	3	4	
3.	I feel tense		1	2	3	4	
4.	I feel strained		1	2	3	4	
5.	I feel at ease		1	2	3	4	
6.	I feel upset		1	2	3	4	
7.	I am presently worryin over possible misf	g ortunes	1	2	3	4	
8.	I feel satisfied		1	2	3	4	
9.	I feel frightened		1	2	3	4	
10.	I feel uncomfortable		1	2	3	4	
11.	I feel self confident		1	2	3	4	
12.	I feel nervous		1	2	3	4	
13.	I feel jittery		1	2	3	4	
14.	I feel indecisive		1	2	3	4	
15.	I am relaxed		1	2	3	4	
16.	I feel content		1	2	3	4	
17.	I am worried		1	2	3	4	
18.	I feel confused		1	2	3	4	
19.	I feel steady		1	2	3	4	
20.	I feel pleasant		1	2	3	4	

Total:

MAYO
P

$\overline{\mathbf{U}}$							
Ι	Copyri Michael	ght © 1995 JL Sullivan					
	PC	; S					

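### The aims promise postoperative adverse events, but endpoint 5 names only perioperative ones and no listed follow-up item or diary row asks about them

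*Combined protocol and SAP*

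**What the plan says.** Under Aims, the variables to be analysed include "adverse intraoperative, perioperative, and postoperative events". The Background closes with the same commitment: "we intend to assess perioperative and postoperative outcomes including safety and pain control".

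The Endpoints list has one safety line, secondary endpoint 5: "Adverse perioperative events cardiovascular parameter changes". It gives no window, definition, grading or method of collection.

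For the three scheduled contacts, Study Design and Methods states that "patients will be evaluated using the Visual Analog Pain Scale (daily maximum and minimum) and visual analogue anxiety scale (daily maximum and minimum"). It adds the pain medication regimen, satisfaction with pain control, and patient-reported duration of anesthetic effect. The Data Analysis Plan, under "Postoperative days 3,7,14 data collection", lists a pain score, an anxiety score and "Analgesic quantities (acetaminophen, meloxicam, ibuprofen, gabapentin, oxycodone, tramadol").

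The diary for postoperative days 1 to 14 has rows for pain scores, tablet counts and free comments. The 3-week follow-up is mentioned only for bringing medication bottles.

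On timing, the Background says liposomal bupivacaine (LB) can "promote local pain control in the postoperative period for up to 72 hours", against half-lives of 1 to 6 hours for traditional agents. The trial is single-blind: the patient does not know the arm and the surgeon does. Follow-up may be done by the performing surgeons, the research coordinator, or both.

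**The concern.** A stated aim has no stated method behind it. The plan sets out how opioid use, pain and anxiety will be collected after surgery, but not how a postoperative adverse event would come to be recorded.

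This matters for two reasons. First, the plan expects the arms to differ in how long the agent acts, so the days after surgery are part of the comparison. Events not asked about then cannot be reliably recovered at analysis. Second, without a standard question the record depends on what patients volunteer and on what the person taking the call writes down. That person may be a surgeon who knows the arm, so recording could differ between arms even if the event rates do not.

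The Background also says the trial should help decide whether the added expense of LB is justified, and it names safety among the outcomes. That use needs comparable postoperative safety data from both arms.

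**Working it through.** The core of this point is a comparison of sections. The plan gives no safety figure to reproduce.

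1. **Aim against endpoint.** The Aims name three categories: intraoperative, perioperative and postoperative. Endpoint 5 names one, perioperative. Endpoints 2, 3 and 4 in the same list are each labelled postoperative, so the authors used that word where they meant it. The Background also separates perioperative from postoperative outcomes.

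2. **Endpoint against collection.**

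| Source | Listed content | Adverse-event item |
|---|---|---|
| Methods, day 3, 7 and 14 contacts | pain, anxiety, pain medication, satisfaction, duration of effect | none |
| Data Analysis Plan, same days | pain, anxiety, analgesic quantities | none |
| Diary, days 1 to 14 | pain scores, tablet counts, free comments | none; comments are unprompted |
| 3-week follow-up | medication bottles | none |
| Attachment 6 | postoperative clinical variables, by title | content not available |

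The diary table is partly broken in the text, but the fragment with a missing label is a tablet-count row. The count is therefore 0 of 3 scheduled contacts with a listed adverse-event item.

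3. **Timing.** The Methods allow the questionnaires to be completed 2 days early or late. The first may therefore be completed on any day from 3 - 2 = 1 to 3 + 2 = 5, and the last from 14 - 2 = 12 to 14 + 2 = 16. Seventy-two hours is 3 days. An undated answer on the first form could not be placed before or after 72 hours, so an added item needs an event date.

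4. **Scale, for illustration only.** The evaluable number is 55 per arm. It reproduces: difference 37.5, SD 60, standardized difference 37.5/60 = 0.625, two-sided alpha 0.05 and 90% power give 54.8 per arm by the noncentral t, rounded up to 55 (power 90.1%). If every patient in an arm were asked and none reported a given event, the exact one-sided 95% upper limit on its rate would be 1 - 0.05^(1/n):
   - n = 55: 1 - 0.05^(1/55) = 5.3%
   - n = 65 (all randomized): 1 - 0.05^(1/65) = 4.5%

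   These limits show what systematic questioning could support. They do not estimate missed events or harm.

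**The case against.** The strongest reply is that much of the apparent gap may come from what cannot be read here. Attachment 6 covers postoperative variables by title and is the natural place for adverse events. Endpoint 5 is ungrammatical, punctuation may have been lost in extraction, and perioperative is never defined. The heading Perioperative Analgesia Protocol stands directly above a 14-day table in the extracted text, so the term may reach past the operation. Patients are in contact three times, have a comments row and return at 3 weeks. Both agents are described as usual practice, and safety is a secondary matter in a trial about opioid use and pain.

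Most of this stands, and it rules out several stronger readings:

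- A reader might infer that LB is released for 72 to 96 hours without safety cover. The documents do not say so. The sentence "This is worn for 72-96 hours postoperatively" describes an information bracelet; the stated LB effect is up to 72 hours.
- A reader might infer that no postoperative safety data will exist at all. That cannot be claimed without attachment 6.
- A reader might take endpoint 5 as limited to the first hours. What the text supports is an undefined window.
- A reader might assume the whole period is spent at home. The Aims allow for some in-hospital time.
- A reader might conclude that the trial observes only the period least able to show an LB-specific harm. No document says when such harms would occur.

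The objection does not remove the mismatch. The Aims and Background both list perioperative and postoperative separately. A list of variables is not in itself a way of asking patients, and a free comments row is not a standard question. Whatever attachment 6 contains, the lists that set out the contacts do not include the item.

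**Conclusion.** The point holds as an inconsistency with a practical consequence. The aims include postoperative adverse events; the safety endpoint does not name them and has no window; and 0 of 3 listed contacts, as well as the diary, ask about them. Conditional on attachment 6 not supplying a method, there is no stated systematic capture of events after the perioperative period, including the rest of the up to 72 hours of LB effect. Volunteered events could then be recorded unevenly by arm, because surgeons are unblinded and may conduct follow-up. That unevenness is a risk inferred from the design; the documents give nothing from which to measure it.

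The point should be fixed, but it is not fatal. It does not touch the opioid primary endpoint, the power calculation or the sample size.

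**What to change.** - Reconcile the Aims, endpoint 5, the contact schedule and attachment 6, so that all four name the same events and the same period.
- Reword endpoint 5 as adverse events from start of surgery through postoperative day 14. Say whether the cardiovascular parameters are part of it or a separate line.
- Add one standard item to the existing day 3, 7 and 14 RedCap questionnaires: any new symptom, emergency visit, readmission or unplanned call since the last contact, with its date. Patients should complete it themselves, since they are the blinded party. Where contact is by phone, the coordinator should read scripted wording.
- Report the events by arm. If a split by time is wanted, use 72 hours, which is the duration the Background gives. Because the last form may come back as early as day 12, state how days 13 and 14 are handled for those patients.

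The cost is one item on three forms and some rewording, with no new visit and no change in sample size. The forms become slightly longer and more minor events will be reported. Some risk of unblinded ascertainment remains if surgeons ask the question themselves.

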Client No.:	Age: Sex: M() F() Date:						
Everyone experie headaches, tooth pain such as illne	iences painful situations at some point in their lives. Such experiences may inc h pain, joint or muscle pain. People are often exposed to situations that may o ess, injury, dental procedures or surgery.	ause					
We are interested in the types of thoughts and feelings that you have when you are in pain. Listed below are thirteen statements describing different thoughts and feelings that may be associated with pain. Using the following scale, please indicate the degree to which you have these thoughts and feelings when you are experiencing pain.							
0 – notatali 1 –	– to a slight degree 2 – to a moderate degree 3 – to a great degree 4 – all	the time					
When	m I'm in pain						
1	I worry all the time about whether the pain will end.						
2	I feel I can't go on.						
3	It's terrible and I think it's never going to get any better.						
4	It's awful and I feel that it overwhelms me.						
5	I feel I can't stand it anymore.						
6	I become afraid that the pain will get worse.						
7	I keep thinking of other painful events.						
8	I anxiously want the pain to go away.						
9	I can't seem to keep it out of my mind.						
10	I keep thinking about how much it hurts.						
11	I keep thinking about how badly I want the pain to stop.						
12	There's nothing I can do to reduce the intensity of the pain.						
13	I wonder whether something serious may happen.						

Perioperative Analgesia Protocol

	POD													
	#1	#2	#3	#4	#5	#6	#7	#8	#9	#10	#11	#12	#13	#14
Minimum nain score														
(scale 0-10)														
(seule o ro)														
Maximum pain score														
(scale 0-10)														
Acetaminophen														
(Tylenol), number of														
tablets used														
Gabapentin														
(Neurontin), number														
of tablets used $(M, 1^{\circ})$														
Meloxicam (Mobic),														
number of tablets used														
of tablets used														
Other comments														
Other comments														
	1	1	1	1	1	1	1	1	1	1	1	1	1	1

Proposed Budget for Exparel IPP study

PERSONNEL (Period 1: 03/01/2021 - 03/01/2023)								
Name	Role			Amount				
	Principal Investigator							
	i inicipai investigator							
	Study Coordinator (12.5%			\$7,875.00				
	x 2 years)							
	Subtotal Direct Cost -			\$7,875.00				
	Personnel							
Internal Services (Period 1: MM/DD/YYYY - MM/DD/YYYY)								
	Entity			Amount				

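### The attached anxiety form takes one current rating, but the secondary anxiety endpoint is a maximum and a minimum; used unchanged at follow-up, the form would not measure that endpoint

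*Combined protocol and SAP*

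**What the plan says.** Four places in the combined protocol and SAP bear on this.

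- **Study Design and Methods.** Patients are "followed-up by phone call or through electronic correspondence (RedCap) on post-operative days 3, 7, and 14", and at those contacts are assessed on the "visual analogue anxiety scale (daily maximum and minimum"). Questionnaires may be completed within 2 days either side.
- **Data Analysis, endpoint list.** Item 4, a secondary endpoint, reads "Postoperative anxiety scores (Maximum and minimum on visual analogue anxiety scale of 0-10) on postoperative days 0-7".
- **Data Analysis, data collection lists.** The visual analogue anxiety score appears under "Postoperative days 3,7,14 data collection" and is tied there to an attachment. The preoperative list holds only the State-Trait Anxiety Inventory and the Pain Catastrophizing scale.
- **Attachments.** The list includes "Visual-analog anxiety scale (attachment 2"). The form itself, under Anxiety Scores, has one part for before the procedure and one for after. Both carry the same instruction: "Mark (X) the point on the scale that best describes how you are feeling at the moment". Its caption reads "Anxiety Level Self-assessment and facial anxiety scale female".

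The patient log for postoperative days 1 to 14 has a row labelled "Maximum pain score" and a matching minimum row. Its other rows are for analgesic tablets and comments.

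**The concern.** A daily maximum and a daily minimum are the two extremes over a period. A mark for the present moment is one point somewhere between them. It identifies neither, and its value depends on when in the day the patient answers. If the attached form is what patients complete after surgery, the trial will hold a different variable from the one it has named as an endpoint. No later analysis can turn one into the other. The pain rows on the log show that the investigators already have a way to capture daily extremes; the anxiety form was not built the same way.

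**Working it through.** The plan states no figure on this point, so the check compares the texts and then counts.

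**Step 1. What is required.** Methods asks for a daily maximum and minimum. Endpoint 4 asks for a maximum and minimum over days 0 to 7 and does not itself say daily. Both need two values, the extremes over a period.

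**Step 2. What the form gives.** One value per completion, for the current state. The text of the form has no recall period, no day label, and no field for a highest or lowest value.

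**Step 3. Whether another form fills the gap.**
- The daily log has minimum and maximum rows for pain only. One row label is partly lost in the extracted text, but what survives refers to tablets, so it is a drug row.
- The State-Trait Anxiety Inventory also asks about the present moment, is a different scale, and is scheduled only before surgery.

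No supplied form records the extremes of anxiety.

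**Step 4. Whether endpoint 4 can be rescued by another reading.** It could mean the highest and lowest of several momentary marks across days 0 to 7. Methods says daily, however, and the scheduled contacts inside that window are days 3 and 7. Two marks on two days give neither a daily range nor a credible range for the week.

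**Step 5. Count of endpoint values per patient.**

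| Reading of the window | Calculation | Values needed | Measured by the form as worded |
|---|---|---|---|
| Daily pair, days 0 to 7 | 8 days × 2 | 16 | 0 |
| Pair at the contacts inside days 0 to 7 (days 3 and 7) | 2 contacts × 2 | 4 | 0 |

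Day 14 is a collection day but lies outside the endpoint window. Even at the early end of the 2-day allowance it falls on day 14 − 2 = 12. It therefore does not belong in the count.

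**Step 6. The window itself.** Endpoint 4 covers 8 days, while collection is on days 3, 7 and 14, of which 2 are in the window. With the allowance, the day 7 questionnaire may be completed as late as day 7 + 2 = 9, also outside it. The existing log starts at day 1, so it covers 7 of the 8 days. Correcting the form alone would leave this conflict in place.

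**The case against.** The strongest reply is that the sheet may not be the question asked at follow-up. Contacts are by telephone or RedCap, and a line to be marked with an X cannot be completed by telephone. The same paragraph of Methods says that the daily maximum and minimum will be assessed, so the RedCap items may already ask for them. The sheet carries no postoperative day label, and its before-and-after layout would suit a comparison around the procedure, which fits the stated aim of analysing pre- and postoperative anxiety. The scale graphic is also not shown.

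Much of this stands. A reader might infer that the maximum and minimum will be missing for every patient at every contact. The documents do not support that unconditionally, because the RedCap and telephone wording is not in them. The reply does not remove the inconsistency: the data collection list ties the anxiety score on days 3, 7 and 14 to an attached scale, and this is the only visual anxiety form supplied. If the real question differs, the attachment still needs correcting.

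A reader might also infer from the caption that scores from a form labelled for women are invalid in a trial of men. The documents show no effect on scores; the faces are offered only as an aid to marking the line, and the figure cannot be seen. It is a minor point to check on the form.

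Finally, anxiety is one of six secondary endpoints, is not in the hypothesis, and plays no part in the power statement. That limits the weight of the point, but the endpoint is still named and still lacks a matching instrument.

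**Conclusion.** The point holds as a mismatch between a secondary endpoint and the instrument supplied for it. If the attached form is used as written at follow-up, none of the 16 values per patient over days 0 to 7 is measured as defined, or none of the 4 at the day 3 and day 7 contacts. The count assumes a pair of values per day, as Methods states, and the window given in endpoint 4; it needs no assumption about effect size or variability. Whether the loss would occur depends on question wording that the documents do not contain. The primary opioid endpoint, the sample size and the pain endpoint are unaffected. The change is worth making before data are collected, because it costs little and the missing values could not be recovered afterwards.

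**What to change.** Either of two changes would close the gap.

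1. Add a minimum anxiety row and a maximum anxiety row, each 0 to 10, to the existing daily log, beside the pain rows. Add a day 0 column, or restate the endpoint window to the days the log covers.
2. Reword the postoperative form and the RedCap and telephone items to ask for the highest and the lowest anxiety over a full stated period, such as the past 24 hours. Asking about today would cut the period off at the time of answering.

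With either change, reconcile the days 0 to 7 window in endpoint 4 with collection on days 3, 7 and 14, and say how questionnaires completed within the 2-day allowance are assigned to a day. Option 2 alone gives values only at the contacts, so the endpoint would then have to be restated to those days. If the investigators in fact want current anxiety, the endpoint and Methods should say so instead. Check the caption of the facial scale at the same time.

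The cost is two short items per day (16 entries per patient over days 0 to 7 under option 1) and an edit to the form and database. No extra visit, staff or patients are needed.
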